### **6.3. Measures to Minimize Bias: Randomization and Blinding**

#### **6.3.1. Allocation to Study Intervention**

This is an open-label study including 2 independent dose cohorts. Randomization and blinding are not applicable. The investigator's knowledge of the treatment should not influence the decision to enroll a particular participant or affect the order in which participants are enrolled.

The investigator will assign participant numbers to the participants as they are screened for the study. Pfizer will provide an allocation schedule to the investigator. The participant will receive the study intervention in compliance with the [SoA](#) and the protocol instruction.

### **6.4. Study Intervention Compliance**

Participants will be dosed at the site. They will receive study intervention directly from the investigator or designee, under medical supervision. The date and time of each dose administered in the CRU will be recorded in the source documents and recorded in the CRF. The dose of study intervention and study participant identification will be confirmed at the time of dosing by a member of the study site staff other than the person administering the study intervention.

The site will complete the required dosage Preparation Record located in the IP manual. The use of the Preparation Record is preferred, but it does not preclude the use of an existing appropriate clinical site documentation system. The existing clinical site's documentation system should capture all pertinent/required information on the preparation and administration of the dose. This may be used in place of the Preparation Record after approval from the sponsor and/or designee.

### **6.5. Dose Modification**

By design, this study only includes administration of single, SC dose of ponsegromab at 2 fixed dosage levels (100 mg and 400 mg). As such, dose modifications will not be made during the study.

### **6.6. Continued Access to Study Intervention After the End of the Study**

No intervention will be provided to study participants at the end of their study participation.

## 6.7. Treatment of Overdose

CCI

The definition of overdose for this trial is based on the operational aspects of the protocol design. Given the nature of this study (ie, SC dose administered in the clinic), and the allowed visit window, an overdose will be defined as more than 4 doses of ponsegromab SC administered.

Sponsor does not recommend specific treatment for an overdose.

In the event of an overdose, the investigator should:

1. Contact the medical monitor within 24 hours.
2. Closely monitor the participant for any AEs/SAEs and laboratory abnormalities for at least 5 half-lives or 28 calendar days after the overdose of ponsegromab (whichever is longer).
3. Document the quantity of the excess dose as well as the time of the overdose in the CRF.
4. Overdose is reportable to Pfizer Safety **only when associated with an SAE**.
5. Obtain a blood sample for PK, CCI [REDACTED] analysis approximately 5-7 days from the date of the last dose of study intervention if requested by the study medical monitor (determined on a case-by-case basis).

## 6.8. Concomitant Therapy

[figure not shown]
Use of prescription or nonprescription drugs and dietary and herbal supplements are prohibited within 7 days or 5 half-lives (whichever is longer) prior to the first dose of study intervention.

Use of marketed or investigational monoclonal antibodies are prohibited within 3 months or 5 half-lives (whichever is longer) prior to the first dose of study medication.

Participants will abstain from all concomitant treatments, except for the treatment of AEs. Limited use of nonprescription medications that are not believed to affect participant safety or the overall results of the study may be permitted on a case-by-case basis following approval by the sponsor.

All concomitant treatments taken during the study must be recorded with indication, daily dose, and start and stop dates of administration. All participants will be questioned about concomitant treatment at each clinic visit.

PFIZER CONFIDENTIAL

Treatments taken within 28 days before the first dose of study intervention will be documented as a prior treatment. Treatments taken after the first dose of study intervention will be documented as concomitant treatments.

## **7. DISCONTINUATION OF STUDY INTERVENTION AND PARTICIPANT DISCONTINUATION/WITHDRAWAL**

### **7.1. Discontinuation of Study Intervention**

Since this is a single-dose study, this section is not applicable.

#### **7.1.1. Potential Cases of Acute Kidney Injury**

Abnormal values in SCr concurrent with presence or absence of increase in BUN that meet the criteria below, in the absence of other causes of kidney injury, are considered potential cases of acute kidney injury and should be considered important medical events.

An increase of  $\geq 0.3$  mg/dL (or  $\geq 26.5$   $\mu$ mol/L) in SCr level relative to the participant's own baseline measurement should trigger another assessment of SCr as soon as practically feasible, preferably within 48 hours from awareness.

If the second assessment (after the first observations of  $\geq 0.3$  mg/dL [or  $\geq 26.5$   $\mu$ mol/L] in SCr relative to the participant's own baseline measurement) is  $\geq 0.4$  mg/dL (or  $\geq 35.4$   $\mu$ mol/L), the participant should be discontinued from the study and adequate, immediate, supportive measures taken to correct apparent acute kidney injury.

Participants should return to the investigator site and be evaluated as soon as possible, preferably within 48 hours from awareness of the second assessment confirming abnormal SCr result. This evaluation should include laboratory tests, detailed history, and physical assessment. In addition to repeating SCr, laboratory tests should include serum BUN, serum creatine kinase, and serum electrolytes (including at a minimum potassium, sodium, phosphate/phosphorus, and calcium), in addition to urinary dipstick, urine microscopic examination, and urinary indices. All cases confirmed on repeat testing as meeting the laboratory criteria for acute kidney injury, with no other cause(s) of laboratory abnormalities identified, should be considered potential cases of drug-induced kidney injury irrespective of availability of all the results of the investigations performed to determine etiology of the abnormal SCr. If  $\geq 2$  healthy participants in a given period/treatment arm are noted to have 2 consecutive SCr results of  $\geq 0.3$  mg/dL (or  $\geq 26.5$   $\mu$ mol/L), an assessment of whether the finding may be considered an adverse drug reaction should be undertaken.

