#### **8.2.5. Clinical Safety Laboratory Assessments**

See [Appendix 2](#) for the list of clinical safety laboratory tests to be performed and the [SoA](#) for the timing and frequency. All protocol-required laboratory assessments, as defined in [Appendix 2](#), must be conducted in accordance with the laboratory manual and the [SoA](#). Unscheduled clinical laboratory measurements may be obtained at any time during the study to assess any perceived safety issues.

The investigator must review the laboratory report, document this review, and record any clinically relevant changes occurring during the study in the AE section of the CRF. Clinically significant abnormal laboratory findings are those which are not associated with the underlying disease, unless judged by the investigator to be more severe than expected for the participant's condition.

All laboratory tests with values considered clinically significantly abnormal during participation in the study or within the time frame before the final planned follow-up visit

PFIZER CONFIDENTIAL

after the last dose of study intervention should be repeated until the values return to normal or baseline or are no longer considered clinically significant by the investigator or medical monitor.

If such values do not return to normal/baseline within a period of time judged reasonable by the investigator, the etiology should be identified and the sponsor notified.

See [Appendix 5](#) for suggested actions and follow-up assessments in the event of potential drug-induced liver injury.

Participants may undergo random urine drug testing at the discretion of the investigator. Urine drug testing conducted prior to dosing must be negative for participants to receive study intervention.

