### 9.3.2. Safety Analyses

All safety analyses will be performed on the Safety Analysis Set. The safety analyses will be presented by cohort.

AEs, ECGs, BP, PR and safety laboratory data will be reviewed and summarized on an ongoing basis during the study to evaluate the safety of participants. Any clinical laboratory, ECG, BP, and PR abnormalities of potential clinical concern will be described. Safety data will be presented in tabular and/or graphical format and summarized descriptively, where appropriate.

Medical history and physical examination collected during the course of the study will be considered source data and will not be required to be reported, unless otherwise noted. However, any untoward findings identified on physical examinations conducted during the active collection period will be captured as AEs, if those findings meet the definition of an AE. Data collected at screening that are used for inclusion/exclusion criteria, such as laboratory data, ECGs, and vital signs, will be considered source data, and will not be required to be reported, unless otherwise noted.

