  - Preexisting AST or ALT baseline values above the normal range: AST or ALT values  $>2$  times the baseline values AND  $>3 \times$  ULN; or  $>8 \times$  ULN (whichever is smaller).
  - Preexisting values of TBili above the normal range: TBili level increased from baseline value by an amount of at least  $1 \times$  ULN **or** if the value reaches  $>3 \times$  ULN (whichever is smaller).

Rises in AST/ALT and TBili separated by more than a few weeks should be assessed individually based on clinical judgment; any case where uncertainty remains as to whether it represents a potential Hy's law case should be reviewed with the sponsor.

The participant should return to the investigator site and be evaluated as soon as possible, preferably within 48 hours from awareness of the abnormal results. This evaluation should include laboratory tests, detailed history, and physical assessment.

In addition to repeating measurements of AST and ALT and TBili for suspected Hy's law cases, additional laboratory tests should include albumin, CK, direct and indirect bilirubin, GGT, PT/INR, total bile acids, and alkaline phosphatase. Consideration should also be given to drawing a separate tube of clotted blood and an anticoagulated tube of blood for further testing, as needed, for further contemporaneous analyses at the time of the recognized initial abnormalities to determine etiology. A detailed history, including relevant information, such as review of ethanol, acetaminophen/paracetamol (either by itself or as a coformulated product in prescription or over-the-counter medications), recreational drug, or supplement (herbal) use and consumption, family history, sexual history, travel history, history of contact with a jaundiced person, surgery, blood transfusion, history of liver or allergic disease, and potential occupational exposure to chemicals, should be collected. Further testing for acute hepatitis A, B, C, D, and E infection, liver imaging (eg, biliary tract), and collection of serum samples for acetaminophen/paracetamol drug and/or protein adduct levels may be warranted.

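### The kidney-injury rule gives two creatinine thresholds without tying them to baseline: the cohort signal reads as an absolute value, and the discontinuation cut-off can be read as one

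*Protocol*

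**What the plan says.** Protocol Section 7.1.1 sets three SCr thresholds.

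- **Repeat test.** An increase of at least 0.3 mg/dL (26.5 µmol/L) over the participant's "own baseline measurement should trigger another assessment of SCr as soon as practically feasible". This one is explicitly a change.
- **Discontinuation.** The sentence opens "If the second assessment (after the first observations of" and its parenthesis goes on to describe a first rise of at least 0.3 mg/dL over baseline. The main clause then says only that the second assessment is at least 0.4 mg/dL (35.4 µmol/L). The consequence is removal from the study and supportive treatment.
- **Cohort signal.** Two or more healthy participants in a period or arm "noted to have 2 consecutive SCr results of" at least 0.3 mg/dL (26.5 µmol/L). Neither an increase nor a baseline is mentioned. The consequence is an assessment of whether the finding is an adverse drug reaction.

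No other section of the protocol or SAP restates or corrects the second or third threshold. SAP Section 3.5.2 defines the laboratory baseline as the last Day -1 value before dosing, so a change can be computed.

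**The concern.** A rule that removes participants and a rule that raises a safety signal should give the intended answer when followed as written. Here the signal threshold is literally an absolute concentration, and the discontinuation threshold can be read as one. The protocol states change criteria in full elsewhere: the liver rule in Appendix 5 has "TBili level increased from baseline value by an amount of at least" one times the upper limit of normal, and the QTcF rule in Section 8.2.4 gives a rise from baseline and an absolute value separately.

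The harm is over-calling. A signal that nearly every cohort meets carries no information. A discontinuation rule applied to a recovered participant ends follow-up early, which mainly endangers t½ and AUCinf, both primary endpoints. Section 9.5 plans 9 enrolled and 8 evaluable per cohort, a margin of one.

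**Working it through.** **Unit check.** With the standard factor 88.4 µmol/L per mg/dL (not given in the documents), 0.3 × 88.4 = 26.5 and 0.4 × 88.4 = 35.4. Both printed pairs are right, so the cut-offs themselves are not misprinted.

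**Which reading is meant.** Let b be the baseline in mg/dL. A value that triggers the repeat test is at least b + 0.3. For any b above 0.1 that already exceeds 0.4, so an absolute 0.4 would ask less of the second test than of the first. At b = 0.9 the trigger value is at least 1.2. Only a rise of 0.4 makes the second step stricter.

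**Does the literal reading miss anyone?** No. A rise of at least 0.4 means a value of at least b + 0.4, which is at least 0.4. The same holds at 0.3. The literal reading can only add cases.

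**Discontinuation rule.** The two readings disagree for every repeat value from 0.4 up to, but not including, b + 0.4. That range contains a repeat equal to baseline whenever b is at least 0.4. No assumption about SCr is needed.

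**Cohort signal.** Let q be the share of participants with two consecutive values of at least 0.3 mg/dL. The documents do not give q. With independent participants, P(at least 2 of n) = 1 − (1−q)^n − nq(1−q)^(n−1).

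| q | n = 9 | n = 8 |
|---|---|---|
| 0.5 | 1 − 10/512 = 98.0% | 1 − 9/256 = 96.5% |
| 0.7 | 99.96% | 99.87% |
| 0.9 | >99.9999% | >99.999% |

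If healthy SCr is assumed to have mean 0.6 to 0.9 and SD 0.12 to 0.20 mg/dL, 93% to 100% of single values are at least 0.3, and the signal probability with n = 9 is about 1.00 throughout. With the threshold read as a rise, and an assumed per-participant chance of 0.1%, 1%, 2% or 5%, the probability is <0.01%, 0.3%, 1.3% or 7.1%.

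**How many participants could reach the discontinuation rule by chance?** The first trigger is a rise under either reading, so this measures exposure to the rule, not the effect of its wording. Assume true SCr b and within-person coefficient of variation CV, both invented for illustration. The chance of a trigger per visit is P(N(0, b·CV·√2) ≥ 0.3), where N(0, s) is normal with SD s. About 9 scheduled post-dose laboratory visits (my count from a partly broken row of the Schedule of Activities, leaving out early termination) times 18 participants gives 162 visits. Expected triggers in the whole study:

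| b (mg/dL) | CV 5% | CV 7.5% | CV 10% |
|---|---|---|---|
| 0.7 | 0.0000001 | 0.004 | 0.20 |
| 0.9 | 0.0002 | 0.14 | 1.5 |
| 1.1 | 0.009 | 0.82 | 4.4 |

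These count visits, not people. Because a participant's visits share one baseline, the top cell corresponds to about 2.6 participants and the central cell to about 0.1.

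**The case against.** The best defence is that the section's own context supplies the meaning. It opens by limiting the rule to abnormal SCr values without another cause of kidney injury. The discontinuation sentence speaks of correcting apparent acute kidney injury, and the next paragraph refers to "awareness of the second assessment confirming abnormal SCr result". A repeat back at a healthy baseline fits none of these. The signal sentence comes directly after "All cases confirmed on repeat testing as meeting the laboratory criteria for acute kidney injury" and reuses a 0.3 figure already given twice as a rise, so it can be taken as shorthand. Other safeguards also exist: "The investigator must review the laboratory report, document this review, and record any clinically relevant changes occurring during the study" (Section 8.2.5), "safety laboratory data will be reviewed and summarized on an ongoing basis during the study" (Section 9.3.2), and prompt discussion of safety issues with the sponsor (Section 8).

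Much of this stands. An experienced investigator would probably infer the intent, and the discontinuation clause is ambiguous rather than plainly wrong. The near-100% signal figures show that the literal rule is unusable, not that a site would apply it. The trigger counts depend on assumed SCr values, and their top cell puts all 18 participants at the extreme. But context shows only what was intended. The signal sentence as written still gives the wrong rule, and Section 8 treats adherence as required and allows no waivers, which does not invite a site to substitute the sensible reading.

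**Conclusion.** The point holds as a minor error. The cohort-signal threshold is wrong as written, and the discontinuation threshold can be read wrongly. In both cases the intent can be inferred.

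The logical results need no assumed SCr values: the literal reading misses no true case, and it would discontinue a participant whose repeat has returned to any baseline of 0.4 mg/dL or more. The 98.0% and 96.5% figures rest on q = 0.5 and independence between participants; a higher q makes the signal fire more often.

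The practical effect is small. The signal rule leads only to an assessment. The discontinuation rule needs a first rise of at least 0.3 mg/dL, so few participants should reach it. On early exit, the samples already drawn and the PK sample at early termination (Section 1.3) remain. No SAP analysis uses these thresholds, and the sample size is unaffected.

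**What to change.** In Protocol Section 7.1.1, reword two clauses and leave the cut-offs alone:

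- Discontinuation: *the second assessment shows an increase of ≥0.4 mg/dL (≥35.4 µmol/L) over the participant's own baseline.*
- Cohort signal: *2 consecutive SCr increases of ≥0.3 mg/dL (≥26.5 µmol/L) over the participant's own baseline.*

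The tiers then fit together. A confirmed rise of 0.3 to below 0.4 mg/dL counts toward the cohort signal without mandatory discontinuation. A second-assessment rise of 0.4 mg/dL or more means discontinuation. The site evaluation, work-up and possible classification as drug-induced kidney injury still apply to confirmed cases.

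The cost is a few words in one protocol section. Visits, samples and analyses do not change.

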### **7.2. Participant Discontinuation/Withdrawal From the Study**

A participant may withdraw from the study at any time at his/her own request. Reasons for discontinuation from the study include the following:

- Refused further study procedures;
- Lost to follow-up;

PFIZER CONFIDENTIAL

- Death;
- Study terminated by sponsor.

At the time of discontinuing from the study, if possible, an early discontinuation visit should be conducted. See the [SoA](#) for assessments to be collected at the time of study discontinuation and follow-up and for any further evaluations that need to be completed.

The early discontinuation visit applies only to participants who are enrolled and then are prematurely withdrawn from the study. Participants should be questioned regarding their reason for withdrawal.

The participant will be permanently discontinued from the study intervention and the study at that time.

If a participant withdraws from the study, he/she may request destruction of any remaining samples taken and not tested, and the investigator must document any such requests in the site study records and notify the sponsor accordingly.

If the participant withdraws from the study and also withdraws consent (see Section 7.2.1) for disclosure of future information, no further evaluations should be performed and no additional data should be collected. The sponsor may retain and continue to use any data collected before such withdrawal of consent.

### **7.2.1. Withdrawal of Consent**

Participants who request to discontinue receipt of study intervention will remain in the study and must continue to be followed for protocol-specified follow-up procedures. The only exception to this is when a participant specifically withdraws consent for any further contact with him or her or persons previously authorized by the participant to provide this information. Participants should notify the investigator in writing of the decision to withdraw consent from future follow-up, whenever possible. The withdrawal of consent should be explained in detail in the medical records by the investigator, as to whether the withdrawal is only from further receipt of study intervention or also from study procedures and/or posttreatment study follow-up, and entered on the appropriate CRF page. In the event that vital status (whether the participant is alive or dead) is being measured, publicly available information should be used to determine vital status only as appropriately directed in accordance with local law.

### **7.3. Lost to Follow up**

A participant will be considered lost to follow-up if he or she repeatedly fails to return for scheduled visits and is unable to be contacted by the study site.

The following actions must be taken if a participant fails to return to the CRU for a required study visit:

- The site must attempt to contact the participant and reschedule the missed visit as soon as possible. Counsel the participant on the importance of maintaining the assigned visit schedule and ascertain whether the participant wishes to and/or should continue in the study;
- Before a participant is deemed lost to follow-up, the investigator or designee must make every effort to regain contact with the participant (where possible, 3 telephone calls and, if necessary, a certified letter to the participant's last known mailing address or local equivalent methods). These contact attempts should be documented in the participant's medical record;
- Should the participant continue to be unreachable, he/she will be considered to have withdrawn from the study.

## 8. STUDY ASSESSMENTS AND PROCEDURES

The investigator (or an appropriate delegate at the investigator site) must obtain a signed and dated ICD before performing any study-specific procedures.

Study procedures and their timing are summarized in the [SoA](#). Protocol waivers or exemptions are not allowed.

Safety issues should be discussed with the sponsor immediately upon occurrence or awareness to determine whether the participant should continue or discontinue study intervention.

Adherence to the study design requirements, including those specified in the [SoA](#), is essential and required for study conduct.

All screening evaluations must be completed and reviewed to confirm that potential participants meet all eligibility criteria. The investigator will maintain a screening log to record details of all participants screened and to confirm eligibility or record reasons for screening failure, as applicable.

Participants will be screened within 28 days prior to administration of the study intervention to confirm that they meet the study population criteria for the study. If the time between screening and dosing exceeds 28 days as a result of unexpected delays (eg, delayed drug shipment), then participants do not require rescreening if the laboratory results obtained prior to first dose administration meet eligibility criteria.

Every effort should be made to ensure that protocol-required tests and procedures are completed as described. However, it is anticipated that from time to time there may be circumstances outside the control of the investigator that may make it unfeasible to perform the test. In these cases, the investigator must take all steps necessary to ensure the safety and

PFIZER CONFIDENTIAL

well-being of the participant. When a protocol-required test cannot be performed, the investigator will document the reason for the missed test and any corrective and preventive actions that he or she has taken to ensure that required processes are adhered to as soon as possible. The study team must be informed of these incidents in a timely manner.

If an IV catheter is utilized for blood sample collections, ECGs and vital sign assessments (PR and BP) should be collected prior to the insertion of the catheter.

For samples being collected and shipped, detailed collection, processing, storage, and shipment instructions and contact information will be provided to the investigator site prior to initiation of the study.

The total blood sampling volume for individual participants in this study is approximately 300 mL. The actual collection times of blood sampling may change. Additional blood samples may be taken for safety assessments at times specified by Pfizer, provided the total volume taken during the study does not exceed 550 mL during any period of 56 consecutive days.

To prepare for study participation, participants will be instructed on the information in the [Lifestyle Considerations](#) and [Concomitant Therapy](#) sections of the protocol.

